8.3. Adverse Events and Serious Adverse Events

Timely, accurate, and complete reporting and analysis of safety information from clinical studies are crucial for the protection of subjects, investigators, and the sponsor, and are mandated by regulatory agencies worldwide. The sponsor has established Standard Operating Procedures in conformity with regulatory requirements worldwide to ensure appropriate reporting of safety information; all clinical studies conducted by the sponsor or its affiliates will be conducted in accordance with those procedures.

Anticipated events will not be recorded and reported in this study as to allow full reporting of AEs from these studies without any special reporting exceptions for individual case safety reports of AEs.

For further details on AEs and SAEs (Definitions and Classifications; Attribution Definitions; Severity Criteria; Special Reporting Situations; Procedures) as well as product quality complaints, refer to [Appendix 1](#), Adverse Events: Definitions and Procedures for Recording, Evaluating, Follow-Up, and Reporting.

Collection of Protocol-Specified Adverse Events of Interest

For any adverse event considered to be one of the following protocol-specified adverse events of interest, and for all deaths, investigators may be asked to provide more detailed information with the source documents or completing the applicable supplemental forms or eCRF.

Cardiovascular Events

Investigators will be instructed to identify the following cardiovascular events of interest:

- MACE (ie, CV death, nonfatal MI, and nonfatal stroke)
- hypotension-related AEs

Pancreatic Events

Investigators will be instructed to identify the following pancreatic events of interest:

- adverse event of pancreatitis
- adverse events of serious or severe abdominal pain leading to suspicion of pancreatitis
- confirmed lipase or amylase elevations $\geq 3 \times$ ULN.

See [Appendix 11](#), Pancreatitis Monitoring and Withdrawal Criteria, for details of how to monitor and document pancreatic adverse events.

Calcitonin Elevation and Thyroid Neoplasm

Investigators will be instructed to identify elevations in calcitonin and possible cases of thyroid hyperplasia, including but not limited to:

- C-cell thyroid hyperplasia
- Medullary thyroid cancer
- Thyroid cancer (papillary, follicular)
- Thyroid nodule
 - See [Appendix 12](#), Guidelines for Calcitonin Monitoring, for details of how to monitor and document thyroid neoplasm.

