Collection of Information on Possible Hypoglycemic Episodes

Subjects will be asked to collect fingerstick glucose determinations at the time of possible hypoglycemic episodes, and to document information on these events, including the fingerstick glucose results, in the blood sugar diary. This diary will be reviewed by study-site personnel at each scheduled visit (see [Appendix 8](#), Hypoglycemia: Definitions, Symptoms and Treatment). Information on possible hypoglycemic episodes will be collected on a separate hypoglycemia eCRF, and hypoglycemic episodes that are considered by the investigator to be adverse events of hypoglycemia should also be recorded on the adverse event eCRF.

8.3.1. Time Period and Frequency for Collecting Adverse Event and Serious Adverse Event Information

All Adverse Events

All adverse events and special reporting situations, whether serious or non-serious, will be reported from the time a signed and dated ICF is obtained until completion of the subject's last study-related procedure, which may include contact for follow-up of safety. Serious adverse events, including those spontaneously reported to the investigator within 5 weeks after the last dose of JNJ64565111/placebo after the last dose of study drug, must be reported using the Serious Adverse Event Form. The sponsor will evaluate any safety information that is spontaneously reported by an investigator beyond the time frame specified in the protocol.

Serious Adverse Events

All SAEs occurring during the study must be reported to the appropriate sponsor contact person by study-site personnel within 24 hours of their knowledge of the event.

Information regarding SAEs will be transmitted to the sponsor using the Serious Adverse Event Form and Safety Report Form of the eCRF, which must be completed and reviewed by a physician from the study site, and transmitted to the sponsor within 24 hours. The initial and follow-up reports of an SAE should be transmitted electronically or by facsimile (fax).

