10.11. Appendix 11: Pancreatitis Monitoring and Withdrawal Criteria

All subjects will be carefully monitored for pancreatitis during the study. Investigators will urge subjects to make an appointment for an unscheduled visit if the subject experiences persistent nausea and/or vomiting for ≥ 3 days, with or without abdominal pain.

Blood samples for analysis of serum amylase and lipase by a central laboratory should be obtained at the visit, and other additional investigations should be performed in order to establish diagnosis, per investigator's discretion.

Study drug should be interrupted immediately if any of the following circumstances occur at any time during treatment:

- If pancreatitis is suspected, or
- Serum amylase ≥ 2 x ULN, or
- Serum lipase ≥ 2 x ULN.

The pancreatic enzyme tests should be repeated within 7 days after the first sample (with both samples analyzed by the central laboratory), and appropriate imaging tests should be performed to establish diagnosis. The results of these tests should be recorded in the source documents.

All subjects with elevated pancreatic enzymes should be followed-up with multiple serum amylase and lipase tests until resolution.

Study drug should be discontinued if acute pancreatitis is confirmed, based on at least 2 of the following 3 signs or symptoms:

- characteristic abdominal pain,
- amylase and/or lipase > 3 x ULN, or
- characteristic findings on CT/MRI.

In any of the circumstances described above occur during the study, the investigator must complete the AE/SAE eCRF page and a Pancreatitis Adverse Event of Special Interest Form. If the event meets the SAE criteria, the information will be transmitted to the sponsor using the Serious Adverse Event Form within 24 hours of the repeat laboratory test.

If a subject discontinues study drug according to the Pancreatitis Monitoring and Withdrawal Criteria then, the event should be recorded as an AE and the reason for withdrawal should be documented as an AE. The subject should be followed to a satisfactory conclusion (ie, until the adverse event resolves, the laboratory value returns to baseline, or the condition becomes stable).

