### **Adverse Events of Interest**

Protocol prespecified AEs of interest included MACE, hypotension-related AEs, pancreatic events, calcitonin elevation, and thyroid neoplasm. Prior to study unblinding, additional AEs of interest were identified including nausea, vomiting, diarrhea, and AEs of injection site reaction. Since investigators may have reported the same clinical condition using different AE terms, prior to study unblinding a list of reported terms that are suggestive of the AEs of nausea, vomiting, diarrhea, injection site reactions, and pancreatic-related AEs was generated. These preferred terms were used to generate a combined analysis for each of these specific AEs of interest.

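### Appendix 11 ties SAE reporting of pancreatic events to the repeat laboratory test, while Section 8.3.1 counts from site knowledge; its form trigger also differs from the enzyme criterion in Section 8.3

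*Protocol*

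**What the plan says.** Four places bear on this.

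- **Protocol Section 8.3.1 (serious adverse events).** All SAEs go to the sponsor "by study-site personnel within 24 hours of their knowledge of the event". The paragraph that follows repeats the 24-hour limit for sending the SAE form. No class of event is exempted.
- **Protocol Appendix 11.** Interruption of study drug is tied to three circumstances: suspected pancreatitis, amylase of at least 2x ULN, or lipase of at least 2x ULN. Enzymes are then repeated within 7 days of the first sample, with both samples read centrally. Discontinuation follows if acute pancreatitis is confirmed on two of three signs or symptoms. The next paragraph says that, should any of the circumstances set out above arise, "the investigator must complete the AE/SAE eCRF page and a Pancreatitis Adverse Event of Special Interest Form". An event that meets SAE criteria is sent to the sponsor "using the Serious Adverse Event Form within 24 hours of the repeat laboratory test".
- **Protocol Section 8.3 (pancreatic events of interest).** There are three categories: an AE of pancreatitis, "adverse events of serious or severe abdominal pain leading to suspicion of pancreatitis", and "confirmed lipase or amylase elevations $\geq 3 \times$ ULN". For events of interest, "investigators may be asked to provide more detailed information with the source documents or completing the applicable supplemental forms or eCRF". The section sends the reader to Appendix 11 "for details of how to monitor and document pancreatic adverse events".
- **SAP Section 6.1 (Adverse Events of Interest) and Attachments 2 and 3.** A list of reported terms for several AEs of interest, ending with "injection site reactions, and pancreatic-related AEs was generated", feeds a combined analysis of each. The list itself is held in a separate file. Attachment 2 counts amylase and lipase values above 2x, 3x and 5x ULN from the laboratory data.

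**The concern.** One set of events has two SAE clocks with different starting points, and the protocol does not say which prevails. A site handling suspected pancreatitis will have Appendix 11 open, because Sections 7.1, 8.2.4 and 8.3 all point there. If it follows the clock printed there, a serious event that it already knows about can wait for a repeat enzyme test. Safety and tolerability is a primary objective, and pancreatitis is among the potential risks named in Section 2.3, so late reporting matters.

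The second issue is which findings oblige a site to complete the AE page and the special-interest form. Appendix 11, taken at its word, sets a lower and unconfirmed enzyme level; Section 8.3 sets a higher and confirmed one. Sites that follow different sections would record the same laboratory finding differently.

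**Working it through.** The plan states no figure to reproduce. The check sets the passages side by side and works out the timing.

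**1. The SAE clock.** Let S be the time of the first enzyme sample, R the time of the repeat, and K the time at which the site knows of the serious event.

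- Section 8.3.1 deadline: K + 24 h.
- Appendix 11 deadline: R + 24 h, with R at most S + 7 days.
- Latest Appendix 11 deadline: S + 7 days + 1 day = S + 8 days (192 h).
- Difference between the two deadlines: R − K.

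| Situation | Section 8.3.1 | Appendix 11 |
|---|---|---|
| Serious event known before the repeat test | K + 24 h | R + 24 h, later by R − K |
| Seriousness first known at the repeat test | K + 24 h | the same time |
| Serious event known, no repeat done | K + 24 h | no deadline |

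If K is no earlier than S and the repeat is on time, R − K lies between 0 and 7 days. Illustration, with assumed timing: a subject is admitted and the site learns of it 2 days after the first sample, and the repeat is drawn on day 7. Section 8.3.1 gives 2 + 1 = day 3, Appendix 11 gives 7 + 1 = day 8, and the gap is 5 days. This takes R as the time of the draw. If the result is meant, the laboratory turnaround is added, and the documents do not state it.

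**2. The form trigger.** Within Appendix 11 the word *circumstances* is used for the interruption list, while the diagnostic items are called signs or symptoms. The literal reading of the form sentence therefore takes in a single value of at least 2x ULN. However, the sentence comes after the diagnostic items, and Section 7.1 calls those same items circumstances. A narrower reading, in which the two-of-three criteria must be met, is possible.

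| Finding | Appendix 11, literal | Appendix 11, narrow | Section 8.3 |
|---|---|---|---|
| One value from 2x to below 3x ULN, normal on repeat | forms required | not required | enzyme category not met |
| Confirmed value from 2x to below 3x ULN | forms required | not required | enzyme category not met |
| Unconfirmed value of at least 3x ULN | forms required | not required | enzyme category not met |
| Confirmed value of at least 3x ULN, no pain or imaging findings | forms required | not required | enzyme category met |
| Pancreatitis on two of three criteria | forms required | required | pancreatitis category met |

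Neither reading of Appendix 11 matches the enzyme category in Section 8.3. The strength of the obligation differs too: Appendix 11 says the forms must be completed, while Section 8.3 says extra detail may be requested. Appendix 12 is more orderly on calcitonin: AE reporting is considered only after a confirmed repeat, at the investigator's assessment.

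**The case against.** **On the clock.** Section 8.3.1 covers all SAEs and nothing in Appendix 11 exempts pancreatitis, so a hospitalised case already falls under the 24-hour rule. A raised enzyme value is not in itself an SAE, and seriousness may only become apparent at the repeat. This stands as far as it goes: the general rule is there and a careful site would follow it. But Appendix 11 gives a different instruction for the same form and the same recipient, and does not say that the general rule prevails.

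A reader might infer that the protocol allows 8 days where Section 8.3.1 allows 1. The documents do not support that comparison. The 8 days run from the first sample and the 1 day from knowledge of the event; the difference between the deadlines is R − K, and it is zero when seriousness first emerges at the repeat.

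**On the trigger.** Section 8.3 sends sites to Appendix 11 for documentation, and Section 8.2.4 sends values of at least 2x ULN to the same appendix for monitoring. Collecting a form below the event definition may be deliberate over-capture, and a site doing so breaks nothing in Section 8.3. That is fair, and a 2x monitoring level alone would not be a conflict. What remains is that the form sentence has two readings and neither agrees with Section 8.3. Section 8.2.4 might be taken as a third standard, but its sentence on recording clinically relevant changes is the general laboratory rule, and the section routes pancreatic enzymes to Appendix 11.

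**On the analysis.** A reader might infer that the SAP's combined pancreatic analysis mixes transient 2x rises with pancreatitis. That cannot be shown: the term list is not in the documents, and Attachment 3 refers to a blinded review of terms before database lock. SAP Section 6.1 tabulates every treatment-emergent AE by preferred term, and Section 6.2 with Attachment 2 reports enzyme limits from laboratory data with their own confidence intervals. Nor is a bias between arms shown, since the trial is double-blind and the same text applies to every arm.

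**Conclusion.** The SAE clock in Appendix 11 is wrong as written and should be corrected. It conflicts with Section 8.3.1 whenever a serious event is known before the repeat test, by R − K. That is at most 7 days if knowledge does not precede the first sample, the repeat is on time, and the clock starts at the draw. With no repeat, Appendix 11 gives no deadline.

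The form trigger is a secondary inconsistency. On the literal reading, values from 2x to below 3x ULN, and unconfirmed values of at least 3x ULN, require forms under Appendix 11 without meeting the enzyme category of Section 8.3. That category is only one of three, so the mismatch does not extend to the whole definition of a pancreatic event of interest. The passages must be reconciled; which threshold is right is not decided here.

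An effect on the combined pancreatic AE count is a risk and no more. The documents give no rate of enzyme rises, so no number of subjects can be attached to it. For scale, the SAP's four-subject filter for showing AE confidence intervals corresponds to 4/47 = 8.5% of a planned arm. That filter is a descriptive screen, and SAP Section 6 plans no hypothesis testing of safety results. The laboratory summaries above 2x, 3x and 5x ULN are unaffected.

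**What to change.** 1. In Appendix 11, delete the clock tied to the repeat test and refer to Section 8.3.1 for SAE reporting. Appendix 1 already does this for product complaints that accompany an SAE.
2. In Appendix 11, name the findings that require the AE page and the special-interest form in place of the general back-reference, and make the laboratory criterion, including whether confirmation is needed, the same as in Section 8.3. The sponsor chooses the criterion. The interruption and discontinuation rules stay as they are.
3. Optional: in the SAP, show pancreatitis terms and enzyme-rise terms on separate rows of the combined pancreatic analysis. Preferred-term tables and laboratory limits already give most of this.

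The cost is a few wording changes in a protocol amendment, with no new procedure or sample. The downside is a one-time check of AE pages already completed against the agreed trigger.

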10.12. Appendix 12: Guidelines for Calcitonin Monitoring

Calcitonin ≥ 10 ng/L and < 20 ng/L

Confounders that can affect calcitonin measurements should be taken into consideration before aggressive diagnostic procedures are undertaken for subjects with calcitonin levels 10 to < 20 ng/L at the screening visit. Specific history should be elicited to identify these confounders. Confounders (ie, drugs [H2 blockers, proton pump inhibitors] other causes of hypergastrinemia [eg, pernicious anemia], smoking, autoimmune thyroiditis, presence of heterophilic antibodies) should be factored into the interpretation of the values on a case-by-case basis. If drugs can be discontinued safely, the screening calcitonin can be repeated after a wash-out period (eg, calcitonin levels return to the normal range by ~ 10 days after stopping proton pump inhibitors).

Calcitonin ≥ 20 ng/L

All calcitonin values ≥ 20 ng/L will be flagged on the laboratory reports from the central laboratory and will be submitted to the sponsor and study site. Subjects will have to undergo a repeat measurement. The timing of the repeat measurement will depend on when the calcitonin value ≥ 20 ng/L was first observed. In particular:

- calcitonin ≥ 20 ng/L on Day 1/Randomization visit: a repeat measurement of calcitonin should be performed preferably within 7 days.
- calcitonin ≥ 20 ng/L at any time after Day 1/Randomization: a repeat measurement of calcitonin should be performed preferably within 2 weeks.

If the repeat calcitonin is confirmed to be ≥ 20 ng/L, the event “elevated calcitonin” should be considered to be reported as an AE per investigator’s assessment if no previously documented elevation of calcitonin prior to study entry.

Depending on the degree of the confirmed calcitonin elevation, additional clinical management or diagnostic procedures should be performed. In particular:

Calcitonin ≥ 20 ng/L and < 50 ng/L

Subjects with calcitonin levels in this range at baseline Day 1 or subsequent visits should have the measurement repeated for confirmation per the suggested window period outlined above. This cohort will provide valuable insights into any potential effect that JNJ-64565111 may have on calcitonin levels in subjects with values above the normal range at baseline. If the repeat value or if any subsequent value measured during the trial is ≥ 50 ng/L then the subject moves into the evaluation category listed above for values ≥ 50 ng/L.

Calcitonin ≥ 50 ng/L and < 100 ng/L

If subjects develop a calcitonin value within this specified range post-randomization, specific medical evaluation will be indicated including a thyroid ultrasound and a pentagastrin stimulation test if available and if not contraindicated (Note: pentagastrin is contraindicated in subjects with known coronary artery disease). Those subjects with positive pentagastrin stimulation tests will be considered to undergo surgery. In the US, where pentagastrin is not available, thyroid ultrasound and fine needle aspiration biopsy may add important clinical information informing the need for surgery.

Calcitonin ≥ 100 ng/L

For any value of ≥ 100 ng/L, the subject should be assumed to have significant C-cell disease and a high likelihood of having medullary carcinoma of the thyroid. Diagnostic evaluation should consist of thyroid ultrasound, fine needle aspiration of any nodules >1 cm and potentially surgery with neck dissection. Family history of medullary thyroid carcinoma or multiple endocrine neoplasia type 2 should be evoked and a rearranged during transfection (RET) proto-oncogene analysis should be undertaken.

NOTE: pg/mL is the conventional unit and ng/L is the SI unit.

10.13. Appendix 13: Instructions for the Completion of PRO Assessments

The following instructions are intended to assist investigators, study coordinators, and those with monitoring responsibilities with the accurate completion of all the PRO questionnaires. For some sites, PRO questionnaires will be completed during scheduled site visits while other PRO questionnaires will be completed at home by the subject. It is therefore important for sites to be familiar with the Time & Events schedule to ensure subjects complete the PROs at the correct setting and visit. Please refer to the PRO Completion Guide for further information.

Site Responsibilities (General)

For this study, we expect that it will take approximately 15 minutes for the subjects to be trained and complete the PROs that are intended to be completed during site visits. For those PROs that are intended to be completed at home, it will take subjects less than 5 minutes a day to complete.

General:

- Never copy PROs from other sources (eg, websites); use only the PRO provided.

Site visit-based assessments, sites must:

- Ensure subject completes the PROs before any clinical assessments are done or results are provided.
- Please have the subject complete the PROs in the same order each time.

Home-based assessments, sites must:

- Ensure subject understands what is expected of them when they return home.
- Distribute the PRO home diary and have the subject review to see if they have questions.
- Have the subject complete the PROs in the order that they appear in the diary.
- Remind the subject to return the PRO home diary at their next scheduled visit.

Preparing the Subject

General:

- Instruct subjects to complete all PRO questionnaires using a blue or black ballpoint pen.
- Explain that all the information on the PROs is confidential, and that someone from the study staff will only check for completeness and not share the results with other clinical staff.
- Explain to subjects the reasons why they are being asked to complete the PROs, ie, they are part of the overall medical assessment and are designed to find out more information about how having their disease has affected their life.
- Allow as much time as the subject needs to orient themselves and complete all PROs.
- Instruct the subjects to:
 - Read the instructions for each questionnaire carefully.
 - Note the recall period for each questionnaire.

- Complete all PROs; Instruct the subject not to skip any questions/or questionnaires.
- Subjects must interpret questions and complete the PROs without input from anyone. If asked for help interpreting or completing the PROs by the subject, please simply reply that there are no right or wrong answers and he/she should use his/her best judgment to complete each question (based on what the subject thinks the question is asking).
- Do not attempt to interpret or explain the instructions, questions, or response options.
- If the subject has difficulty choosing between 2 response options, simply state “choose the answer that most closely matches your experience.”

Site visit-based assessments:

- Provide a quiet, private or semi-private location for the subject to complete the PROs.
- Ensure subjects have access to study staff for questions.

Home-based assessments:

- Instruct the subject to complete each daily assessment at the same time each day, in the same setting each day, for the following 7 consecutive days.
- These questionnaires are administered at home because of the concepts being measured and the period of recall.

Quality Control

- Complete the subject number, visit date and time on every PRO questionnaire.

Site visit-based assessments:

- Before the subject leaves:
 - Check for any questions that might have been skipped/left blank.
 - If an item has been skipped, point this out to the subject and ask them to complete.
 - If an item has more than one response, ask the subject to reconsider the question and try to choose the answer that most closely matches their experience.

Home-based assessments:

- Before the subject leaves the appropriately scheduled site visit, distribute the PRO home diary, provide instructions for completion, and remind subject to return the booklet at the next scheduled site visit.
- Questionnaires in the diary should be completed by the subject daily for the next 7 consecutive days.
- Upon the subject’s return for their next scheduled site visit, collect the PRO home diary from the subject and check for completeness.

Special Issues

- Subjects should be instructed to complete the PROs without input from anyone. However, if a subject cannot read the PROs or complete it/them independently (eg, due to visual impairment, limited literacy, or difficulty with pens), then a designated person can read the

items and response choices aloud and mark the appropriate response choices as verbally stated by the subject.

- The designated person should read each question in its entirety in a neutral voice, avoiding any cues, even if interrupted by the subject with an answer. The designated person should repeat each of the subject's answers, eg, "A little bit." The subject should not be prompted by the designated person in any other way. No help should be offered to the subject in interpreting the questionnaire.
- If a person is designated to assist the subject with the PROs, this person should remain consistent across assessment questionnaires and across assessment periods.
- If a designated person assists the subject with the PROs, this should be noted in the Footer section on the first page of each PRO assessment instrument.

